### 7.3 Statistical Analysis

The primary analysis will include all patients who are eligible for this study and who undergo planned neurosurgery. PPV and NPV will be estimated and the 95% confidence interval associated with each measure will be provided. Secondary analysis will take advantage of multiple biopsies taken from areas representing a range of fluorescence intensity within each patient. The Spearman's rank correlation coefficient will be calculated to assess the correlation between fluorescent intensity as scored by the neurosurgeon and the tumor content as scored by the pathologist. To account for within-patient correlation, the Cochran-Mantel-Haenszel Chi-Squared test will be used to test the association between fluorescence intensity and tumor content.

All patients who are enrolled and take 5-ALA will be considered evaluable for toxicity. Since potential adverse events related to 5-ALA are known to be transient in nature, it is felt that a 14-day evaluation window is relevant to assess the safety profile of this agent. The formal analysis and final report of toxicities will be performed when all patients have been enrolled and followed for toxicities for 14 days after administration of 5-ALA. Reporting of adverse events is described in Section 6. We intend to monitor adverse events on a monthly basis to determine if there are unacceptable toxicities. A report of all adverse events since the first subject was enrolled will be prepared every month, along with a tabular display of the relative frequency of all grade 2 or higher toxicities considered possibly, probably, or likely related to 5-ALA. This information will be submitted to the UCSF-CCC Data Safety Monitoring Committee (DSMC) who is responsible for monitoring data quality and patient safety for all UCSF-CCC institutional clinical studies.

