#### *Toxicity*

Confidential

*In vivo* pharmacological and toxicological effects that may be associated with elevated systemic levels of ALA, Pp IX, and other intermediates of porphyrin biosynthesis in humans are well known, and characterize a group of metabolic diseases known as the porphyrias. An association between high systemic concentrations of ALA and neurological abnormalities is observed in Acute Intermittent Porphyria (AIP). However, attempts at clarifying the association between elevated ALA and the neurological symptoms of AIP have led to inconsistent results and contradictory conclusions. Most studies have shown that ALA and Porphobilinogen (PBG equals condensation of 2 molecules of ALA) are not neurotoxic *in vivo* when administered in large amounts to animals and humans. Concentration of these precursors in the brain or cerebrospinal fluid (CSF) of porphyric patients is substantially below that required for demonstrable toxicity *in vitro*. Litman and Correia, 1985, hypothesized that depletion of hepatic heme, as seen in AIP, leads to elevated tryptophan content and 5-hydroxytryptamine turnover in the brain, and is responsible for the neurological symptoms of AIP (17). On this basis then, administration of exogenous ALA would not lead to a depletion of hepatic heme and, therefore, would not be expected to elicit the neurological symptoms of AIP. Photosensitivity, associated with high systemic levels of Pp IX, is a typically finding in Erythropoietic Protoporphyrinemia (EPP) which is associated with decreased activity of ferrochelatase, the enzyme that converts Pp IX to heme. EPP is entirely cutaneous, with none of the hemolytic or neurological problems of other porphyrias.

Mild transient nausea and occasional vomiting have been observed following oral administration of high doses of ALA. Webber et al. 1997, observed that almost one-quarter of all patients who retained ALA had at least one abnormality in liver function tests (18). Nausea and vomiting were seen in 20% of the patients but no other symptoms of porphyria.

The most common complaint, due to Pp IX photosensitization, is very unpleasant pricking, itching or burning sensation under the skin after exposure to the sun. A systemic load above 10 mg/kg is required to develop skin photosensitization (DUSA Pharmaceuticals/Sun Pharma), which lasts from approximately 24 to 48 hours following ALA administration.

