### 5.2 Surgical Procedure

ALA will be mixed in the minimum volume of sterile water or juice immediately before use and given as a single bolus orally approximately 3 hours prior to scheduled anesthesia. Image-guided microsurgical resection of the tumor will be undertaken. Following the standard tumor resection under light microscopy, the residual tumor bed will be illuminated with blue light via a high pass optical filter in the microscopes light chain. The surgeon will examine the tumor bed with a barrier filter in the optical chain of the surgical microscope. The surgeon will quantitatively measure the concentration of Pp IX by placing the intraoperative fluorescence/reflectance probe in gentle contact with brain tissue by the surgeon for 3-5 seconds to make a recording. If fluorescence is present, and if safe, small biopsies will be taken from those areas of fluorescence as well as from non-fluorescing regions in the tumor resection cavity. When possible, the intent would be to collect a number of biopsies with a range of fluorescence intensities from each patient (at least one biopsy from normal-appearing tissues and at least one from the most fluorescent area). All biopsy specimens, including those taken from the bulk tumor, will be reviewed by a neuropathologist to assess tumor content. The expectation is that residual fluorescent tissue in the tumor cavity will be surgically removed (if deemed safe by the

neurosurgeon), potentially leading to more complete tumor resection. Pathologic confirmation of tumor type will be made by neuropathology.

Biopsies of fluorescent and non-fluorescent tissue within the tumor cavity will be graded by the surgeon at the time of biopsy as 0 to 3 fluorescence. A screen shot of the fluorescent image of the resected tumor illuminated with blue light via a high-pass filter will be documented for each patient with an integrating video camera. The fluorescence intensity and the quantitative measurement obtained with the intraoperative probe corresponding to each area on the screen shot from which biopsy is taken will be recorded by the surgeon in the operating room. The sample will be snap frozen in the operating room and provided to the pathologist for grading the tumor from 0 to 3 based on the degree of cellular infiltration. The scale to be used for grading is as follows:

Grade	Surgeon (intensity of fluorescence)	Pathologist (cell density)
0	No fluorescence	No tumor cell density content

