## **7 STATISTICAL CONSIDERATIONS**

### **7.1 Study Endpoints**

This is a single-center, single arm, open label phase II trial of fluorescence-guided resection by use of 5-aminolevulinic (ALA) at a dose of 20 mg/kg body weight in glioma patients. We hypothesize that surgical removal of the residual fluorescent tissues in the tumor cavity, presumably representing tumorous cells, will result in an increase in the amount of tumor removal during neurosurgical resection. In addition, we hypothesize that for recurrent malignant glioma, that the fluorescent material will reflect active viable tumor and not changes related to treatment such as macrophages or gliosis.

The primary analysis will be based on one biopsy taken from the most fluorescent area and one from normal appearing tissues for each patient as judged by the neurosurgeon.

The endpoints of interest in this study are as follows:

- Primary Endpoint: Positive Predictive Value (PPV), defined as the percentage of biopsies taken from the most fluorescent tissues determined by the pathologist as having tumorous content.
- Second Endpoints:
  - Negative Predictive Value (NPV), defined as the percentage of biopsies taken from non-fluorescent tissues determined as having no tumor content by the pathologist.
  - The safety of the use of 5-aminolevulinic (ALA) at a dose of 20 mg/kg body weight for neurosurgical resection in glioma patients
  - The correlation between fluorescent intensity as scored by the neurosurgeon and the tumor content as scored by the pathologist
  - The percentage of patients for whom there is no fluorescent tissue after surgery

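### The efficacy set in Section 7.3 has no 5-ALA intake condition, so patients without effective exposure can raise the no-fluorescence percentage, add uninformative data to NPV and weaken the fixed rule of 44

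*Combined protocol and SAP*

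**What the plan says.** Section 7.3 defines the efficacy set by eligibility and surgery: "The primary analysis will include all patients who are eligible for this study and who undergo planned neurosurgery". PPV and NPV are to be estimated in it with 95% confidence intervals. For safety, the same section adds a condition: "All patients who are enrolled and take 5-ALA will be considered evaluable for toxicity".

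The endpoints in Section 7.1 have different units.

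- PPV is per biopsy: "the percentage of biopsies taken from the most fluorescent tissues determined by the pathologist as having tumorous content".
- NPV is per biopsy: "the percentage of biopsies taken from non-fluorescent tissues determined as having no tumor content by the pathologist".
- The last secondary endpoint is per patient: "The percentage of patients for whom there is no fluorescent tissue after surgery". It has no dosing condition, no analysis set of its own and no success criterion.

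The drug is a single oral dose about 3 hours before anesthesia (5.1, 5.2). Vomiting is an expected effect (6.4.1). The Toxicity part of 3.1 reports from one cited study: "Nausea and vomiting were seen in 20% of the patients but no other symptoms of porphyria". No section says how a missed, partial or vomited dose is handled in the efficacy analyses.

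**The concern.** Fluorescence can inform about tumour only if the drug reached the tissue. A cavity that is dark because little or no 5-ALA was absorbed says nothing about residual tumour, yet under the literal wording of 7.3 the patient remains in the efficacy set. Three results could be affected: the percentage with no residual fluorescence, NPV together with the fluorescence-pathology correlation, and the primary decision rule, which is a fixed count.

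The toxicity sentence shows that an intake condition was within the authors' reach, so its absence from the efficacy set leaves a real ambiguity. The trial is open label. If the question is left open, exclusions for poor exposure would be decided after the surgeon has seen whether the cavity fluoresced.

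**Working it through.** **Inputs from the documents.** 50 patients per cohort, PPV 80% under the null, target 92%, one-sided exact binomial test at 0.10, about 90% power, and a cut of 44 (all 7.2).

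**Assumption.** u = number of patients in a cohort of 50 without effective exposure. The documents give no such rate, so u = 1, 3, 5 and 10 are shown. The value 10 is 20% of 50. It borrows the combined nausea and vomiting figure in 3.1 and serves only as an upper bound.

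**Step 1: the plan's own figure.** P(X ≥ 44) for n = 50 is 0.8981 at PPV 92%, which reproduces the stated 90%. At PPV 80% it is 0.1034, slightly above the nominal 0.10. A cut of 45 gives 0.0480 and power 0.7919.

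**Step 2: no residual fluorescence.** With t the rate in exposed patients, and every unexposed patient counted as having no fluorescence, the reported rate is (u + (50 − u)t)/50. The shift is u(1 − t)/50, which is never downward.

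| t (assumed) | u = 1 | u = 3 | u = 5 | u = 10 |
|---|---|---|---|---|
| 50% | 51% | 53% | 55% | 60% |
| 70% | 70.6% | 71.8% | 73% | 76% |

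**Step 3: NPV.** Suppose each patient gives one non-fluorescent biopsy, and let q be the tumour-free share among unexposed patients. The shift is then u(q − NPV)/50.

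| NPV in exposed (assumed) | q (assumed) | u = 1 | u = 5 | u = 10 |
|---|---|---|---|---|
| 70% | 30% | 69.2% | 66% | 62% |
| 50% | 50% | 50% | 50% | 50% |
| 50% | 70% | 50.4% | 52% | 54% |

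The sign follows q − NPV. If no biopsy is taken from such patients, the shift is zero. The documents conflict on whether one is taken. The narrative in 5.2 is conditional: "If fluorescence is present, and if safe, small biopsies will be taken from those areas of fluorescence as well as from non-fluorescing regions". The list of surgeon responsibilities in 5.2 asks for at least one non-fluorescent biopsy without that condition. Section 7.1 bases the primary analysis on "one biopsy taken from the most fluorescent area and one from normal appearing tissues for each patient as judged by the neurosurgeon".

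**Step 4: the primary rule.** A patient without a fluorescent biopsy is not in the PPV denominator, so the proportion is unaffected. That patient also cannot add to the count of 44. With n = 50 − u biopsies:

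| Fluorescent biopsies | Power, cut fixed at 44 | Type I error, cut fixed at 44 | Smallest cut with error ≤ 0.10 | Power at that cut |
|---|---|---|---|---|
| 50 | 0.898 | 0.1034 | 45 | 0.792 |
| 49 | 0.805 | 0.0547 | 44 | 0.805 |
| 47 | 0.475 | 0.0093 | 42 | 0.829 |
| 45 | 0.115 | 0.0005 | 40 | 0.852 |
| 40 | 0 | 0 | 36 | 0.787 |

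Most of the power loss comes from holding the count fixed, not from the smaller number of biopsies.

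**The case against.** The best defence is that 7.1 describes a trial of fluorescence-guided resection using ALA, and 5.2 opens the surgical procedure with giving the drug. Planned neurosurgery may therefore be meant to include dosing. An all-operated set is also a defensible inclusive choice. This is a fair reading of intent, but the text does not state it, and it leaves partial and vomited doses unaddressed.

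Other parts of the defence stand, and they limit the point. A reader might infer the following, which the documents do not support:

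- **That undosed patients are successes by rule.** The quoted sentence governs the primary analysis. The no-fluorescence percentage has neither a success criterion nor a stated set, so the effect arises only if the same set is used.
- **That NPV is biased downward.** The shift needs a biopsy, on which the sections conflict, and its direction depends on an unknown tumour-free rate.
- **That a fifth of doses are lost.** The 20% is nausea and vomiting combined, from one cited study. A patient who vomits may already have absorbed part of the dose.
- **That vomiting goes unrecorded.** Section 6.4 collects all adverse events from dosing. What the documents do not describe is a record of the amount taken, or of the timing of vomiting relative to induction.

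The size is also modest at low loss. One patient moves a 50% rate by 1 point, against a 95% half-width of about 14 points (1.96 × √(0.5 × 0.5/50) = 0.139).

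**Conclusion.** The point holds in limited form. Section 7.3 omits from the efficacy set the intake condition that it applies to toxicity, and nothing settles how incomplete exposure is analysed.

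- The no-fluorescence percentage rises by about 1 point per unexposed patient in a cohort of 50. This assumes a 50% rate in exposed patients and use of the same set.
- NPV and the correlation may gain uninformative grade-0 results, if biopsies are taken. The NPV shift may go either way.
- PPV as a proportion is not biased. The largest effect is on the fixed count: power at PPV 92% falls from 0.898 to 0.805 with one missing fluorescent biopsy and to 0.475 with three.

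How often this would happen cannot be determined from the documents. The change is worth making because it is cheap and is best settled before fluorescence results are known.

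**What to change.** 1. In 7.3, define the efficacy set for PPV, NPV, the correlation and the no-fluorescence percentage as eligible patients with documented 5-ALA intake who undergo the planned surgery. Evaluability should rest on the dosing record and not on whether the cavity fluoresced.
2. Record the amount taken and the time of any vomiting before induction.
3. Report these endpoints with and without patients whose dose was incomplete or vomited. An intake condition alone keeps patients who vomit, so this comparison is what addresses them. Report the all-operated set as a sensitivity analysis.
4. In 7.2, give the cut-off by number of evaluable fluorescent biopsies, and say whether 0.10 is a strict limit, since 44 of 50 has exact error 0.1034.
5. Reconcile the biopsy wording in the 5.2 narrative, the 5.2 responsibilities list and 7.1, so that it is clear whether a patient without fluorescence gives an NPV biopsy.

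The cost is a few sentences, two data items and one or two extra tables. The evaluable number may fall slightly below 50 per cohort. Keeping 50 evaluable would mean enrolling 50/(1 − d), rounded up: 52, 54, 56 or 63 for an assumed loss d of 2%, 6%, 10% or 20%. No dosing or re-dosing rule is proposed.
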